2.5.4 Windows for time points

For the purpose of changes over time analyses, select assessments will be assigned analysis visits by comparing actual visit dates with target visit dates and pre-defined visit windows. Specific algorithms in the assignments of the analysis visits such as the target study days and the corresponding visit windows are listed in Appendix B.

2.5.5 Unscheduled visits

Unscheduled visit measurements of laboratory data, vital signs, and ECG will be included in the by-visit summaries if scheduled visit measurements are not available. If unscheduled visit happened on the same day of the scheduled visit in lab, the average value of those measurements will be used. The unscheduled visit measurements will be used for computation of baseline and PCSAs.

2.5.6 Pooling of centers for statistical analyses

Investigation of the effects of geographic regions may be performed on an exploratory basis.

2.5.7 Statistical technical issues

Not applicable.

3 INTERIM ANALYSIS

A clinical study report will be produced at study completion. An interim report will also be produced if a sub-study analysis of data is performed to support regional regulatory requirements.

4 DATABASE LOCK

The database is planned to be locked at 30 days after last patient last visit.

5 SOFTWARE DOCUMENTATION

All summaries and statistical analyses will be generated using SAS Version 9.4 or higher.

7 LIST OF APPENDICES

[Appendix A](#): Potentially clinically significant abnormalities (PCSA) criteria

[Appendix B](#): Visit windows

Appendix A Potentially clinically significant abnormalities criteria

Table 5 - Criteria for potentially clinically significant abnormality

Measures	Adult Criteria	Pediatric Criteria
Liver function tests		
ALT	>3 x ULN	≥3 x ULN
	>5 x ULN	≥5 x ULN
	>10 x ULN	≥10 x ULN
	>20 x ULN	≥20 x ULN
AST	>3 x ULN	≥3 x ULN
	>5 x ULN	≥5 x ULN
	>10 x ULN	≥10 x ULN
	>20 x ULN	≥20 x ULN
Alkaline Phosphatase	>1.5 x ULN	≥1.5 x ULN
Total Bilirubin	>1.5 x ULN	≥1.3 x ULN
	>2 x ULN	
ALT and Total Bilirubin	ALT >3 x ULN and Total Bilirubin >2 x ULN	ALT ≥3 x ULN and Total Bilirubin ≥2 x ULN
Hematology		
White Blood Cell (WBC)	<3.0 GIGA/L (non-Black), <2.0 GIGA/L (Black), ≥16.0 GIGA/L	Birth/0 to 27 days old (Neonates) <4.0 GIGA/L ≥25.0 GIGA/L 28 days/1 month to 23 months old (Infants) <4.0 GIGA/L ≥20.0 GIGA/L 24 months/2 years to <6 years old (Children) >3.0 GIGA/L ≥16.0 GIGA/L 6 to <12 years old (Children) <5.0 GIGA/L ≥17.0 GIGA/L 12 to 16/18 years old (Adolescents) <4.5 GIGA/L ≥13.5 GIGA/L

Measures	Adult Criteria	Pediatric Criteria
Lymphocytes	>4.0 GIGA/L	Birth/0 to 27 days old (Neonates) <1.2 GIGA/L >17.0 GIGA/L 28 days/1 month to 23 months old (Infants) <2.0 GIGA/L >13.5 GIGA/L 24 months/2 years to <6 years old (Children) <1.0 GIGA/L >9.5 GIGA/L 6 to <12 years old (Children) <1.0 GIGA/L >8.0 GIGA/L 12 to 16/18 years old (Adolescents) <0.6 GIGA/L >6.0 GIGA/L
Neutrophils	<1.5 GIGA/L (non-Black) <1.0 GIGA/L (Black)	Birth/0 to 27 days old (Neonates) <4.0 GIGA/L (1 day old) <1.5 GIGA/L (2 – 7 days old) <1.25 GIGA/L (>7 day – 1 month old) >1 ULN 28 days/1 month to 23 months old (Infants) <1.0 GIGA/L (1 – 3 months) <1.2 GIGA/L (3 – 24 months) >1 ULN 24 months/2 years to <6 years old (Children) <1.2 GIGA/L >1 ULN 6 to <12 years old (Children) <1.2 GIGA/L >1 ULN 12 to 16/18 years old (Adolescents) <1.2 GIGA/L >1 ULN
Monocytes	>0.7 GIGA/L	
Basophils	>0.1 GIGA/L	
Eosinophils	>0.5 GIGA/L or >ULN if ULN \geq 0.5 GIGA /L	>0.5 GIGA/L Or >ULN if ULN >0.5 GIGA/L

Measures	Adult Criteria	Pediatric Criteria
Hemoglobin	Males: $\leq 115 \text{ g/L}$ ($\leq 7.14 \text{ mmol/L}$), $\geq 185 \text{ g/L}$ ($\geq 11.48 \text{ mmol/L}$) Females: $\leq 95 \text{ g/L}$ (5.9 mmol/L), $\geq 165 \text{ g/L}$ (10.24 mmol/L) Decrease from Baseline: $\geq 20 \text{ g/L}$ (1.24 mmol/L)	Birth/0 to 27 days old (Neonates) $<86 \text{ mmol/L}$ or 12.0 g/dL or any decrease $> 0.31 \text{ mmol/L}$ or 2 g/dL 28 days/1 month to 23 months old (Infants) $<1.40 \text{ mmol/L}$ or 9.0 g/dL or any decrease $> 0.31 \text{ mmol/L}$ or 2 g/dL 24 months/2 years to <16/18 years old (Children, Adolescents) $<1.55 \text{ mmol/L}$ or 10.0 g/dL or any decrease $> 0.31 \text{ mmol/L}$ or 2 g/dL
Hematocrit	Males : $\leq 0.37 \text{ v/v}$, $\geq 0.55 \text{ v/v}$ Females : $\leq 0.32 \text{ v/v}$, $\geq 0.5 \text{ v/v}$	Birth/0 to 27 days old (Neonates) $<0.39 \text{ l/l}$ or 40% $>0.61 \text{ l/l}$ or 47% 28 days/1 month to 23 months old (Infants) $<0.29 \text{ l/l}$ or 29% $>0.42 \text{ l/l}$ or 42% 24 months/2 years to <16/18 years old (Children, Adolescents) $<0.32 \text{ l/l}$ or 32% $>0.47 \text{ l/l}$ or 47%
RBC	$\geq 6 \text{ TERA/L}$	
Platelets	$<100 \text{ GIGA/L}$ $\geq 700 \text{ GIGA/L}$	$<100 \text{ GIGA/L}$ $>700 \text{ GIGA/L}$

ECG – PCSA criteria

HR	<50 bpm	Birth/0 to 27 days old (Neonates)
	<50 bpm and decrease from baseline ≥ 20 bpm	≤ 90 bpm and decrease from baseline ≥ 20 bpm
	<40 bpm	≥ 190 bpm and increase from baseline
	<40 bpm and decrease from baseline ≥ 20 bpm	≥ 20 bpm
	<30 bpm	28 days/1 month to 23 months old (Infants)
	<30 bpm and decrease from baseline ≥ 20 bpm	≤ 80 bpm and decrease from baseline
		≥ 20 bpm
	>90 bpm	≥ 175 bpm and increase from baseline
	>90 bpm and increase from baseline ≥ 20 bpm	≥ 20 bpm
	>100 bpm	24 months/2 years to <6 years old (Children)
PR	>100 bpm and increase from baseline ≥ 20 bpm	≤ 75 bpm and decrease from baseline
	>120 bpm	≥ 20 bpm
	>120 bpm and increase from baseline ≥ 20 bpm	≥ 140 bpm and increase from baseline
		≥ 20 bpm
		6 to <12 years old (Children)
		≤ 50 bpm and decrease from baseline
		≥ 20 bpm
		≥ 120 bpm and increase from baseline
		≥ 20 bpm
		12 to 16/18 years old (Adolescents)
QRS		≤ 50 bpm and decrease from baseline
		≥ 20 bpm
		≥ 120 bpm and increase from baseline
		≥ 20 bpm
		Birth/0 to 27 days old (Neonates) ≥ 120 ms
QRS	>200 ms	28 days/1 month to 23 months old (Infants) ≥ 140 ms
	>200 ms and increase from baseline $\geq 25\%$	24 months/2 years to <6 years old (Children) ≥ 160 ms
	>220 ms	6 to <12 years old (Children) ≥ 170 ms
	>220 ms and increase from baseline $\geq 25\%$	12 to 16/18 years old (Adolescents) ≥ 180 ms
	>240 ms	
QRS	> 240 ms and increase from baseline $\geq 25\%$	
	>110 ms	Birth/0 to 27 days old (Neonates) ≥ 85 ms
	>110 msec and increase from baseline $\geq 25\%$	28 days/1 month to 23 months old (Infants) ≥ 85 ms
	>120 ms	24 months/2 years to <6 years old (Children) ≥ 95 ms
	>120 ms and increase from baseline $\geq 25\%$	6 to <12 years old (Children) ≥ 100 ms
QRS		12 to 16/18 years old (Adolescents) ≥ 110 ms

QTc (either QTcF or QTcB)	Absolute values (ms) >450 ms >480 ms >500 ms	Birth/0 to <12 years old (Neonates, Infants, Children) Absolute values (ms) Borderline: 431 – 450 ms Prolonged*: >450 ms Additional: ≥500 ms AND Increase from baseline 30-60 ms >60 ms
		Increase from baseline Borderline: Increase from baseline 30 – 60 ms Prolonged*: Increase from baseline >60 ms
		12 to 16/18 years old (Adolescents) Absolute values (ms) Borderline: 431 – 450 ms (Boys);451 – 470 ms (Girls) Prolonged*: >450 ms (Boys);>470 ms (Girls) Additional: ≥500 ms AND Increase from baseline Birth/0 to <12 years old (Neonates, Infants, Children) Absolute values (ms) Borderline: 431 – 450 ms Prolonged*: >450 ms Additional: ≥500 ms AND Increase from baseline Borderline: Increase from baseline 30 – 60 ms Prolonged*: Increase from baseline >60 ms
		12 to 16/18 years old (Adolescents) Absolute values (ms) Borderline: 431 – 450 ms (Boys);451 – 470 ms (Girls) Prolonged*: >450 ms (Boys);>470 ms (Girls) Additional: ≥500 ms AND Increase from baseline Borderline: Increase from baseline30 – 60 ms Prolonged*: Increase from baseline >60 ms

*QTc prolonged and ΔQTc >60 ms are the PCSA to be identified in individual subjects/patients listings.

Clinical chemistry

Creatinine	$\geq 150 \mu\text{mol/L}$ (Adults) $\geq 30\%$ increase from baseline $\geq 100\%$ increase from baseline	Birth/0 to <6 years old (Neonates, Infants, Children) $\geq 53 \mu\text{mol/L}$ or 0.6 mg/dL 6 years to <12 years old (Children) $\geq 90 \mu\text{mol/L}$ or 1.1 mg/dL 12 years to 16/18 years old (Adolescents) $\geq 132 \mu\text{mol/L}$ or 1.5 mg/dL
Blood Urea Nitrogen	$\geq 17 \text{ mmol/L}$	Birth/0 to 27 days old (Neonates) $\geq 4.3 \text{ mmol/L}$ or 12 mg/dl 28 days/1 month to 16/18 years old (Infants, Children, Adolescents) $\geq 6.4 \text{ mmol/L}$ or 18 mg/dl
Chloride	$<80 \text{ mmol/L}$ $\geq 115 \text{ mmol/L}$	$\leq 80 \text{ mmol/L}$ $\geq 115 \text{ mmol/L}$
Sodium	$\leq 129 \text{ mmol/L}$ $\geq 160 \text{ mmol/L}$	$\leq 129 \text{ mmol/L}$ $\geq 150 \text{ mmol/L}$
Potassium	$<3 \text{ mmol/L}$ $\geq 5.5 \text{ mmol/L}$	Birth/0 to 27 days old (Neonates) $\leq 3.0 \text{ mmol/L}$ $\geq 7.0 \text{ mmol/L}$ 28 days/1 month to 23 months old (Infants) $\leq 3.5 \text{ mmol/L}$ $\geq 6.0 \text{ mmol/L}$ 24 months/2 years to 16/18 years old (Children, Adolescents) $\leq 3.5 \text{ mmol/L}$ $\geq 5.5 \text{ mmol/L}$
Glucose		
Hypoglycemia	$\leq 3.9 \text{ mmol/L}$ and $<\text{LLN}$	$<2.7 \text{ mmol/L}$
Hyperglycemia	$\geq 11.1 \text{ mmol/L}$ (unfasted); $\geq 7 \text{ mmol/L}$ (fasted)	$\geq 7 \text{ mmol/L}$ (fasted after >12 hours of fast); $\geq 10.0 \text{ mmol/L}$ (unfasted)
Albumin	$\leq 25 \text{ g/L}$	

Vital signs

Heart rate	≤ 50 bpm and decrease from baseline ≥ 20 bpm ≥ 120 bpm and increase from baseline ≥ 20 bpm	Birth/0 to 27 days old (Neonates) ≤ 90 bpm and decrease from baseline ≥ 20 bpm ≥ 190 bpm and increase from baseline ≥ 20 bpm 28 days/1 month to 23 months old (Infants) ≤ 80 bpm and decrease from baseline ≥ 20 bpm ≥ 175 bpm and increase from baseline ≥ 20 bpm 24 months/2 years to <6 years old (Children) ≤ 75 bpm and decrease from baseline ≥ 20 bpm ≥ 140 bpm and increase from baseline ≥ 20 bpm 6 to <12 years old (Children) ≤ 50 bpm and decrease from baseline ≥ 20 bpm ≥ 120 bpm and increase from baseline ≥ 20 bpm 12 to 16/18 years old (Adolescents) ≤ 50 bpm and decrease from baseline ≥ 20 bpm ≥ 120 bpm and increase from baseline ≥ 20 bpm
Systolic BP	≤ 95 mmHg and decrease from baseline ≥ 20 mmHg ≥ 160 mmHg and increase from baseline ≥ 20 mmHg	Birth/0 to 27 days old (Neonates) ≤ 60 mmHg and decrease from baseline ≥ 20 mmHg ≥ 85 mmHg and increase from baseline ≥ 20 mmHg 28 days/1 month to 23 months old (Infants) ≤ 70 mmHg and decrease from baseline ≥ 20 mmHg ≥ 98 mmHg and increase from baseline ≥ 20 mmHg 24 months/2 years to <6 years old (Children) ≤ 70 mmHg and decrease from baseline ≥ 20 mmHg ≥ 101 mmHg and increase from baseline ≥ 20 mmHg 6 to <12 years old (Children) ≤ 80 mmHg and decrease from baseline ≥ 20 mmHg ≥ 108 mmHg and increase from baseline ≥ 20 mmHg 12 to 16/18 years old (Adolescents) ≤ 90 mmHg and decrease from baseline ≥ 20 mmHg ≥ 119 mmHg and increase from baseline ≥ 20 mmHg

Diastolic BP	≤ 45 mmHg and decrease from baseline ≥ 10 mmHg ≥ 110 mmHg and increase from baseline ≥ 10 mmHg	Birth/0 to 27 days old (Neonates) ≤ 34 mmHg and decrease from baseline ≥ 10 mmHg ≥ 50 mmHg and increase from baseline ≥ 10 mmHg 28 days/1 month to 23 months old (Infants) ≤ 34 mmHg and decrease from baseline ≥ 10 mmHg ≥ 54 mmHg and increase from baseline ≥ 10 mmHg 24 months/2 years to <6 years old (Children) ≤ 34 mmHg and decrease from baseline ≥ 10 mmHg ≥ 59 mmHg and increase from baseline ≥ 10 mmHg 6 to <12 years old (Children) ≤ 48 mmHg and decrease from baseline ≥ 10 mmHg ≥ 72 mmHg and increase from baseline ≥ 10 mmHg 12 to 16/18 years old (Adolescents) ≤ 54 mmHg and decrease from baseline ≥ 10 mmHg ≥ 78 mmHg and increase from baseline ≥ 10 mmHg
--------------	---	--

Appendix B Visit windows

The analysis visits are assigned by comparing the distance between the calculated study day of each assessment (defined as time elapsed from the start of study drug in the TDR12857 study till the time of the assessment) with the listed target study days and the corresponding analysis windows of the applicable group of assessments, utilizing the general rules below:

1. If more than one non-missing values are assigned to the same analysis visit, then the assessment performed closest to the target study day will be used in the by-visit analysis.
2. Multiple values assessed on the same date will be averaged prior to being assigned an analysis visit.
3. If two assessments are assessed on different dates but equidistant from the target date, the values assessed on a later date will be used.
4. Use a combination of 2 & 3 in cases where there are multiple records equidistant from the target study day. For example, for a post-baseline visit, if there are 2 records, 7 days before the infusion and 3 records 7 days after the infusion, then take the 3 records after the infusion and average them for analysis value.

All visits in the applicable datasets will be used, including scheduled and unscheduled visits. (For change from TDR12857 baseline analyses, rebaseline visit and assessments performed after rebaseline will be handled in the same manner.) Note that baseline is defined as the latest available observation before the first infusion in the TDR12857.

Table 1 — Analysis windows for 6MWT, PFTs, ECG, hematology, and urinalysis:

VISIT (target study day*)	Analysis Visit	Analysis Visit Window (in study days*)
Baseline	Baseline	
Week 1@ in TDR (1)	Week 1	1 to 42 days
Week 13 in TDR (85)	Week 13	43 to 127 days
Week 25 in TDR (169)	Week 25	128 to 273 days/(1 st day of LTS – 1)**
Month 6 in LTS (365)	Week 52	(1 st day of LTS) to 456 days
Month 12 in LTS (547)	Week 78	457 to 638 days
Month 18 in LTS (730)	Week 104	639 to 821 days
Month 24 in LTS (912)	Week 130	822 to 1003 days
Month 30 in LTS (1095)	Week 156	1004 to 1186 days
Month 36 in LTS (1277)	Week 182	1187 to 1368 days
Month 42 in LTS (1460)	Week 208	1369 to 1551 days
Month 48 in LTS (1642)	Week 234	1552 to 1733 days
Month 54 in LTS (1825)	Week 260	1734 to 1916 days
Month 60 in LTS (2007)	Week 286	1917 to 2098 days
Month 66 in LTS (2190)	Week 312	2099 to 2281 days
Month 72 in LTS (2372)	Week 338	2282 to 2402 days

@ Week 1 visit only applies to ECG, hematology, and urinalysis.

*Study days are days since the first infusion in the TDR12857 study.

**For patients who enrolled in LTS13769, the upper boundary of the window is 273 days or (1st day of LTS – 1), whichever is earlier; for patients who didn't enroll in LTS13769, use study day 273 as cutoff.

Table 2 – Immunogenicity (anti-alglucosidase alfa IgG antibody) – Group 2 patients only

VISIT (target study day*)	Analysis Visit	Analysis Visit Window (in study days*)
Baseline/Week 1	Baseline	
Week 25 in TDR (169)	Week 25	92 to 273 days/(1 st day of LTS – 1)**
Month 6 in LTS (365)	Week 52	(1 st day of LTS) to 456 days
Month 12 in LTS (547)	Week 78	457 to 638 days
Month 18 in LTS (730)	Week 104	639 to 821 days
Month 24 in LTS (912)	Week 130	822 to 1003 days
Month 30 in LTS (1095)	Week 156	1004 to 1186 days
Month 36 in LTS (1277)	Week 182	1187 to 1368 days
Month 42 in LTS (1460)	Week 208	1369 to 1551 days
Month 48 in LTS (1642)	Week 234	1552 to 1733 days
Month 54 in LTS (1825)	Week 260	1734 to 1916 days
Month 60 in LTS (2007)	Week 286	1917 to 2098 days
Month 66 in LTS (2190)	Week 312	2099 to 2281 days
Month 72 in LTS (2372)	Week 338	2282 to 2402 days

*Study days are days since the first infusion in the TDR12857 study.

**For patients who enrolled in LTS13769, the upper boundary of the window is 273 days or (1st day of LTS – 1), whichever is earlier; for patients who didn't enroll in LTS13769, use study day 273 as cutoff.

Table 3 – Immunogenicity (anti-avalglucosidase alfa [neoGAA] antibodies)

VISIT (target study day*)	Analysis Visit	Analysis Visit Window (in study days*)
Baseline/Week 1	Baseline	
Week 5 in TDR (35)	Week 5	23 to 50 days
Week 9 in TDR (63)	Week 9	51 to 78 days
Week 13 in TDR (91)	Week 13	79 to 106 days
Week 17 in TDR (119)	Week 17	107 to 134 days
Week 21 in TDR (148)	Week 21	135 to 163 days
Week 25 in TDR (176)	Week 25	164 to 183 days
Week 27 in TDR (190)	Week 27	184 to 198 days/(1 st day of LTS - 1)
Month 1 in LTS (213)	Week 32	(1 st day of LTS) to 228 days
Month 2 in LTS (244)	Week 36	229 to 259 days
Month 3 in LTS (274)	Week 40	260 to 289 days
Month 4 in LTS (304)	Week 44	290 to 319 days
Month 5 in LTS (335)	Week 48	320 to 350 days
Month 6 in LTS (365)	Week 52	351 to 411 days
Month 9 in LTS (456)	Week 65	412 to 502 days
Month 12 in LTS (547)	Week 78	503 to 594 days
Month 15 in LTS (639)	Week 91	595 to 685 days
Month 18 in LTS (730)	Week 104	686 to 776 days
Month 21 in LTS (821)	Week 117	777 to 867 days
Month 24 in LTS (912)	Week 130	868 to 959 days
Month 27 in LTS (1004)	Week 143	960 to 1050 days
Month 30 in LTS (1095)	Week 156	1051 to 1141 days
Month 33 in LTS (1186)	Week 169	1142 to 1232 days

VISIT (target study day*)	Analysis Visit	Analysis Visit Window (in study days*)
Month 36 in LTS (1277)	Week 182	1233 to 1324 days
Month 39 in LTS (1369)	Week 195	1325 to 1415 days
Month 42 in LTS (1460)	Week 208	1416 to 1506 days
Month 45 in LTS (1551)	Week 221	1507 to 1597 days
Month 48 in LTS (1642)	Week 234	1598 to 1689 days
Month 51 in LTS (1734)	Week 247	1690 to 1780 days
Month 54 in LTS (1825)	Week 260	1781 to 1871 days
Month 57 in LTS (1916)	Week 273	1872 to 1962 days
Month 60 in LTS (2007)	Week 286	1963 to 2054 days
Month 63 in LTS (2099)	Week 299	2055 to 2145 days
Month 66 in LTS (2190)	Week 312	2146 to 2236 days
Month 69 in LTS (2281)	Week 325	2237 to 2327 days
Month 72 in LTS (2372)	Week 338	2328 to 2402 days

*Study days are days since the first infusion in the TDR12857 study.

**For patients who enrolled in LTS13769, the upper boundary of the window is 273 days or (1st day of LTS – 1), whichever is earlier; for patients who didn't enroll in LTS13769, use study day 273 as cutoff.

Table 4 – Biochemistry

VISIT (target study day*)	Analysis Visit	Analysis Visit Window (in study days*)
Baseline	Baseline	
Week 1 in TDR (1)	Week 1	1 to 8 days
Week 3 in TDR (15)	Week 3	9 to 21 days
Week 5 in TDR (29)	Week 5	22 to 35 days
Week 7 in TDR (43)	Week 7	36 to 49 days
Week 9 in TDR (57)	Week 9	50 to 63 days
Week 11 in TDR (71)	Week 11	64 to 77 days
Week 13 in TDR (85)	Week 13	78 to 91 days
Week 15 in TDR (99)	Week 15	92 to 105 days
Week 17 in TDR (113)	Week 17	106 to 119 days
Week 19 in TDR (127)	Week 19	120 to 133 days
Week 21 in TDR (142)	Week 21	134 to 148 days
Week 23 in TDR (156)	Week 23	149 to 162 days
Week 25 in TDR (169)	Week 25	163 to 176 days/(1 st day of LTS – 1)**
Day 1/Week 0 in LTS (183)	Week 28	(1 st day of LTS) to 198 days
Month 1 in LTS (213)	Week 32	199 to 228 days
Month 2 in LTS (244)	Week 36	229 to 259 days
Month 3 in LTS (274)	Week 40	260 to 289 days
Month 4 in LTS (304)	Week 44	290 to 319 days
Month 5 in LTS (335)	Week 48	320 to 350 days
Month 6 in LTS (365)	Week 52	351 to 380 days
Month 7 in LTS (396)	Week 56	381 to 411 days
Month 8 in LTS (426)	Week 61	412 to 441 days

VISIT (target study day*)	Analysis Visit	Analysis Visit Window (in study days*)
Month 9 in LTS (456)	Week 65	442 to 471 days
Month 10 in LTS (487)	Week 69	472 to 502 days
Month 11 in LTS (517)	Week 74	503 to 532 days
Month 12 in LTS (547)	Week 78	533 to 562 days
Month 13 in LTS (578)	Week 82	563 to 593 days
Month 14 in LTS (609)	Week 87	594 to 624 days
Month 15 in LTS (639)	Week 91	625 to 654 days
Month 16 in LTS (670)	Week 96	655 to 685 days
Month 17 in LTS (700)	Week 100	686 to 715 days
Month 18 in LTS (730)	Week 104	716 to 745 days
Month 19 in LTS (761)	Week 108	746 to 776 days
Month 20 in LTS (791)	Week 112	777 to 806 days
Month 21 in LTS (821)	Week 117	807 to 836 days
Month 22 in LTS (852)	Week 121	837 to 867 days
Month 23 in LTS (883)	Week 126	868 to 898 days
Month 24 in LTS (912)	Week 130	899 to 927 days
Month 25 in LTS (944)	Week 134	928 to 959 days
Month 26 in LTS (974)	Week 139	960 to 989 days
Month 27 in LTS (1004)	Week 143	990 to 1019 days
Month 28 in LTS (1035)	Week 147	1020 to 1050 days
Month 29 in LTS (1065)	Week 152	1051 to 1080 days
Month 30 in LTS (1095)	Week 156	1081 to 1110 days
Month 31 in LTS (1126)	Week 160	1111 to 1141 days
Month 32 in LTS (1157)	Week 165	1142 to 1172 days

VISIT (target study day*)	Analysis Visit	Analysis Visit Window (in study days*)
Month 33 in LTS (1186)	Week 169	1173 to 1201 days
Month 34 in LTS (1218)	Week 173	1202 to 1233 days
Month 35 in LTS (1248)	Week 178	1234 to 1263 days
Month 36 in LTS (1277)	Week 182	1264 to 1324 days
Month 39 in LTS (1369)	Week 195	1325 to 1415 days
Month 42 in LTS (1460)	Week 208	1416 to 1506 days
Month 45 in LTS (1551)	Week 221	1507 to 1597 days
Month 48 in LTS (1642)	Week 234	1598 to 1689 days
Month 51 in LTS (1734)	Week 247	1690 to 1780 days
Month 54 in LTS (1825)	Week 260	1781 to 1871 days
Month 57 in LTS (1916)	Week 273	1872 to 1962 days
Month 60 in LTS (2007)	Week 286	1963 to 2054 days
Month 63 in LTS (2099)	Week 299	2055 to 2145 days
Month 66 in LTS (2190)	Week 312	2146 to 2236 days
Month 69 in LTS (2281)	Week 325	2237 to 2327 days
Month 72 in LTS (2372)	Week 338	2328 to 2402 days

*Study days are days since the first infusion in the TDR12857 study.

**For patients who enrolled in LTS13769, the upper boundary of the window is 176 days or (1st day of LTS – 1), whichever is earlier; for patients who didn't enroll in LTS13769, use study day 176 as cutoff.

Table 5 – Urine Hex4

VISIT (target study day*)	Analysis Visit	Analysis Visit Window (in study days*)
Baseline	Baseline	
Week 1 in TDR (1)	Week 1	1 to 8 days
Week 3 in TDR (15)	Week 2	9 to 21 days
Week 5 in TDR (29)	Week 5	22 to 35 days
Week 7 in TDR (43)	Week 7	36 to 49 days
Week 9 in TDR (57)	Week 9	50 to 63 days
Week 11 in TDR (71)	Week 11	64 to 77 days
Week 13 in TDR (85)	Week 13	78 to 91 days
Week 15 in TDR (99)	Week 15	92 to 105 days
Week 17 in TDR (113)	Week 17	106 to 119 days
Week 19 in TDR (127)	Week 19	120 to 133 days
Week 21 in TDR (142)	Week 21	134 to 148 days
Week 23 in TDR (156)	Week 23	149 to 162 days
Week 25 in TDR (169)	Week 25	163 to 176 days/(1 st day of LTS – 1)**
Month 6 in LTS (365)	Week 52	(1 st day of LTS) to 548 days
Month 18 in LTS (730)	Week 104	549 to 913 days
Month 30 in LTS (1095)	Week 156	914 to 1278 days
Month 42 in LTS (1460)	Week 208	1279 to 1643 days
Month 54 in LTS (1825)	Week 260	1644 to 2008 days
Month 66 in LTS (2190)	Week 312	2009 to 2373 days
Month 72 in LTS (2372)	Week 338	2374 to 2402 days

*Study days are days since the first infusion in the TDR12857 study.

**For patients who enrolled in LTS13769, the upper boundary of the window is 176 days or (1st day of LTS – 1), whichever is earlier; for patients who didn't enroll in LTS13769, use study day 176 as cutoff.

Table 6 – Plasma concentration of avalglucosidase alfa

VISIT (target study day*)	Analysis Visit	Analysis Visit Window (in study days*)
Baseline	Baseline	
Week 1 in TDR (1)	Week 1	1 to 42 days
Week 13 in TDR (85)	Week 13	43 to 127 days
Week 25 in TDR (169)	Week 25	128 to 273 days/(1 st day of LTS – 1)**
Month 6 in LTS (365)	Week 52	(1 st day of LTS) to 548 days
Month 18 in LTS (730)	Week 104	549 to 913 days
Month 30 in LTS (1095)	Week 156	914 to 1278 days
Month 42 in LTS (1460)	Week 208	1279 to 1643 days
Month 54 in LTS (1825)	Week 260	1644 to 2008 days
Month 66 in LTS (2190)	Week 312	2009 to 2373 days
Month 72 in LTS (2372)	Week 338	2374 to 2402 days

*Study days are days since the first infusion in the TDR12857 study.

**For patients who enrolled in LTS13769, the upper boundary of the window is 273 days or (1st day of LTS – 1), whichever is earlier; for patients who didn't enroll in LTS13769, use study day 273 as cutoff.

Table 7 –MRI, muscle biopsy

VISIT (target study day*)	Analysis Visit	Analysis Visit Window (in study days*)
Baseline	Baseline	
Week 27 in TDR (184)	Week 27	92 to 273 days/(1 st day of LTS – 1)**
Month 24 in LTS (365)	Week 52	(1 st day of LTS) to 1278 days
Month 48 in LTS (1095)	Week 156	1279 to 2008 days
Month 72 in LTS (2372)	Week 338	2009 to 2402 days

*Study days are days since the first infusion in the TDR12857 study.

**For patients who enrolled in LTS13769, the upper boundary of the window is 273 days or (1st day of LTS – 1), whichever is earlier; for patients who didn't enroll in LTS13769, use study day 273 as cutoff.

Other assessments not specified above, if presented in by-visit summary tables, will use the recorded visits, rather than defined analysis visits.

By visit analyses of changes over time from rebaseline will use the rebased visits recorded.

Signature Page for
lts13769-16-1-9-sap

Approve & eSign	[Name] Clinical 26-Mar-2020 21:03:03 GMT+0000
-----------------	---

Approve & eSign	[Name] Clinical 27-Mar-2020 18:21:06 GMT+0000
-----------------	---

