9.2 PHARMACOKINETICS

9.2.1 Sampling times

Blood samples for evaluation of avalglucosidase alfa PK will be collected before, during, and after avalglucosidase alfa infusions at 6 months and then yearly thereafter for the first 6 years.

Sampling times are as follows: pre-dose (prior to infusion), at the end of the infusion, and at 1, 4, 8, 12, and 24 hours after infusion. The following PK blood samples are to be collected within 15 minutes of scheduled time: pre-dose and all samples immediately following the end of the infusion through 8 hours post infusion. Pharmacokinetic samples collected 12 hours through 24 hours post infusion are to be collected ± 2 hours of the scheduled time.

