2.4.6 Analyses of pharmacokinetic variables

All the pharmacokinetic parameters described in [Section 2.1.5](#) will be analyzed using the pharmacokinetic population.

Individual assessments and descriptive statistics (mean, standard deviation [SD], median, minimum, maximum, geometric mean, and percent coefficient of variation [CV%]) will be presented for plasma concentration time data and PK parameters for each dose level and visit. Individual and mean (SD) plasma concentration time profile will be presented graphically for each visit.

To evaluate the effect of immunogenicity on the PK of avalglucosidase alfa, the following plots will be presented:

- Individual profiles of avalglucosidase alfa concentrations over time at 6-month visit and yearly thereafter, grouped by patient/dose group and ADA status (ever positive, always negative, baseline ADA positive [preexisting ADA], neutralizing antibody positive)
- Median (SD) trough avalglucosidase alfa concentrations over time at 6-month visit and yearly thereafter, grouped by patient/dose group and ADA status (ever positive, always negative, baseline ADA positive [preexisting ADA], neutralizing antibody positive)

If relationships are apparent, further quantitative/statistical analysis may be performed (eg, statistical significance, correlation coefficients).

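### SAP Appendix B rules 1 and 2, as written, reduce the seven serial PK concentrations of an infusion to one value, which contradicts the profiles and trough plots required by SAP 2.4.6

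*SAP*

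**What the plan says.** SAP Appendix B assigns analysis visits by comparing study days with target days and "the corresponding analysis windows of the applicable group of assessments, utilizing the general rules below". One of the listed groups is "Table 6 – Plasma concentration of avalglucosidase alfa".

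- **Rule 2:** "Multiple values assessed on the same date will be averaged prior to being assigned an analysis visit".
- **Rule 1:** where several values fall in one analysis visit, "then the assessment performed closest to the target study day will be used in the by-visit analysis".
- **Way out:** the closing text of Appendix B sends only assessments not listed in its tables to the recorded visits. Plasma concentration is listed, so this does not cover it.

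Protocol 9.2.1 schedules a pre-dose sample, then samples "at the end of the infusion, and at 1, 4, 8, 12, and 24 hours after infusion". That is seven concentrations per PK infusion.

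SAP 2.4.6 states that descriptive statistics "will be presented for plasma concentration time data and PK parameters for each dose level and visit". It also asks for individual and mean (SD) concentration-time profiles at each visit, and for plots of trough concentration over time by patient/dose group and ADA status.

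SAP 2.1.5 has Cmax, AUC, CL and the other parameters calculated by noncompartmental methods from the plasma concentrations.

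**The concern.** The Appendix B rules suit assessments with one intended value per visit, such as a walk test or a hematology panel. Repeats on one day are then replicates, and averaging them is harmless. Serial PK samples are different: same-date values are meant to differ, because they trace a rise and a decline. Neither rule is limited to samples taken at the same nominal time.

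Long-term PK is part of the primary objective in both documents, and the profile and trough plots are the SAP's stated means of judging how immunogenicity affects PK. A programmer who follows Appendix B cannot produce them. A programmer who produces them must depart from Appendix B, and the SAP does not say what replaces rules 1 and 2 for Table 6 or how samples dated the day after the infusion are assigned.

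**Working it through.** The documents give no figure to reproduce here. The check applies the two rules literally to the sampling schedule.

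**Step 1: which samples share a date.** Nominal times come from Protocol 9.2.1. The protocol gives neither infusion length in hours nor clock times, so end-of-infusion times from 10:00 to 20:00 are assumed. A sample falls on the next date if end time plus nominal hours reaches 24:00.

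| Infusion ends | Infusion date | Next date |
|---|---|---|
| 10:00–11:59 | pre-dose, end, 1, 4, 8, 12 h | 24 h |
| 12:00–15:59 | pre-dose, end, 1, 4, 8 h | 12, 24 h |
| 16:00–19:59 | pre-dose, end, 1, 4 h | 8, 12, 24 h |
| 20:00 | pre-dose, end, 1 h | 4, 8, 12, 24 h |

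The 24 h sample is on the next date throughout; the 12 h and 8 h samples depend on when the infusion ends. The ±2 h allowance for the later samples can move the noon boundary by up to two hours.

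**Step 2: rule 2.** All values on each date are averaged, so seven concentrations become two values.

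**Step 3: rule 1.** Let d be infusion day minus target day. The infusion date is |d| days from target and the next date is |d + 1| days.

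- d ≥ 0: |d| < |d + 1|. The infusion-date average is kept and the next-date samples are dropped.
- d ≤ −1: |d + 1| < |d|. The next-date average is kept, and pre-dose, end of infusion and all other infusion-date samples are dropped.

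No whole number gives |d| = |d + 1|, so ties do not arise. Over d = −14 to +14, the width of the protocol's PK visit window, 15 of 29 offsets keep the infusion date and 14 keep the next date. This counts offsets and is not a forecast: the protocol window is set around the patient's own LTS13769 schedule, while Table 6 counts days from the first TDR12857 infusion.

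In either case, seven concentrations become one value per patient-visit. This needs no assumption about half-life.

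**Step 4: what the one value represents (illustration only).** Assume C(t) = 100 × 0.5^(t / half-life), a pre-dose value of 0, and an infusion ending between 12:00 and 15:59.

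- Half-life 2 h: infusion-date mean = (0 + 100 + 70.7 + 25 + 6.25)/5 = 40.4% of the end-of-infusion value. Next-date mean = (1.56 + 0.02)/2 = 0.79%. Ratio about 51.
- Half-life 4 h: infusion-date mean = (0 + 100 + 84.1 + 50 + 25)/5 = 51.8%. Next-date mean = (12.5 + 1.56)/2 = 7.0%. Ratio about 7.

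At 0.5 h and 1 h the infusion-date means are 25.1% and 31.3%, and the next-date means are close to zero. The protocol's animal half-lives run from about 0.3 to 1.99 h, and the monkey values come from the first elimination phase only. The documents give no human half-life.

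**Step 5: compare with SAP 2.4.6.** A profile needs values at separate nominal times, and a trough plot needs the pre-dose value alone. After rules 1 and 2, the trough has been either averaged with the peak or discarded.

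**The case against.** The strongest reply is that nobody would program it this way. SAP 2.4.6 is the specific PK section and plainly expects whole profiles, so Table 6 is best read as labelling the visit to which a profile belongs. SAP 2.5.4 also confines the windows to analyses of change over time, which a within-infusion profile is not. And rule 2 cannot be fully literal: Table 1 of Appendix B puts pulmonary function tests under the same rules, and no one would average supine with standing FVC.

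Much of this stands. The intention is probably as described, and the text does not show a settled plan to collapse profiles. But supine and standing FVC are different parameters, whereas serial concentrations are repeated values of one listed analyte, so keeping parameters apart does not settle the PK case. The trough plot over successive visits is a change-over-time analysis even on the narrow reading of 2.5.4. The SAP does not say which section yields.

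A reader might also infer that Cmax, AUC and clearance are distorted. The documents do not support that: SAP 2.1.5 derives them from the plasma concentrations and nothing there refers to windowed values. A reader might further quote a 50-fold difference between the two possible values, or a loss of half of the profiles. The first depends on an assumed half-life of 2 h or less and falls to about 7-fold at 4 h. The second depends on visit timing symmetric about target, which is stated nowhere.

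**Conclusion.** The contradiction is real and should be corrected. As written, Appendix B turns the seven scheduled concentrations of a PK infusion into one value per visit, and the side of the target day on which the infusion falls decides which samples are lost. The concentration-time statistics, profiles and trough plots of SAP 2.4.6 cannot be produced from data handled that way.

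The collapse to one value follows from the rules and the sampling schedule, given that the infusion ends on the date it starts. Which samples land on the next date depends on clock times that the documents do not give. The percentages and ratios are illustrations under an assumed single-exponential decline. The defect is a missing condition on the rules for Table 6; harm to the noncompartmental parameters is not shown.

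**What to change.** Add to SAP Appendix B that, for Table 6:

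1. the analysis window is assigned once per PK profile, by infusion date;
2. all samples of that profile, including those dated the next day, take that analysis visit;
3. rules 1 to 4 choose between profiles when more than one falls in a window;
4. averaging applies only to replicates at the same nominal time.

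Concentration summaries are then by visit and nominal time, and all seven concentrations are kept, in line with SAP 2.4.6. The cost is a few sentences of SAP text and a nominal-time key in the windowing program. No new data are needed.
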